2.6 Benefits to Participants

Potential benefits to participants include helping healthcare providers determine the most efficacious mode of local anaesthetic administration through an ACC. This may lead to changes in care pathways at Counties-Manukau Health and could have considerable benefits for future patients undergoing TKA. Depending on the individual's mindset, the participation in clinical research can lead to considerable satisfaction. As there is no control or placebo group, active therapeutic interventions will not be withheld, participants are not at risk of missing out on the therapeutic benefit of an ACC.

For both the District Health Board and the wider anaesthetic community, the results of this study could provide some clarification to changes which may be required in our pathways for patient care after TKA. Should benefits be seen in mobilisation, satisfaction or hospital length of stay, there are obvious economic effects including the reduction in overall healthcare costs and improved compliance with rehabilitation protocols.

3. Statistical Considerations

The statistical assessment of trial data will be devised and performed by a biostatistician. Patient demographic, surgical and anaesthetic factors will be recorded and tabulated. Demographic data will be presented as number (percentage) for discrete observation and mean (standard deviation) for continuous parameters.

For primary outcome (analgesic consumption in oral morphine equivalents) a test for differences in means / variances will be performed as guided by the data. Statistical test will be two-tailed with $p=0.05$ used as the threshold for statistical significance. Where possible, the clinical relevance of a statistical test will be provided in addition to the p-value. Similar testing strategies will be used for the secondary outcomes with differences in discrete observations (e.g. yes/no data) determined using the Fisher Exact test.

4. Data collection and retention

Data collection will be performed primarily by a research nurse specialist and/or investigator who will visit postoperatively to obtain the necessary parameters on paper form – this will be stored inside a secure cabinet in the department of anaesthesia and pain medicine. A Microsoft Excel spread sheet will be designed with various worksheets for data collection and analysis – this will be password protected and only accessed by approved investigators from within the Counties Manukau Health network.

Only those involved in the study will have access to study data. The study data will be kept for a minimum of 10 years as required by the Retention of Health Information's

regulations 1996. We have no plans beyond this study to use any information obtained – should this change; additional consent will be sought.

5. Ethics and Responsibility

This study will be conducted in strict compliance to protocol and with the approval of the local research review committee. The investigators, [name] and [name], can declare that they do not have any financial or other interests in the study.

6. Conclusion

This study aims to identify the superior technique of local anaesthetic delivery down an adductor canal catheter after a primary total knee arthroplasty. This study will allow us to examine and optimise our local care pathways for patients undergoing TKA, as well as inform and influence other healthcare providers further afield.

7. Bibliography

1. Prevention CfDca. Number of all-listed procedures for discharges from short-stay hospitals, by procedure category and age: United States, 2010 [Webpage].
http://www.cdc.gov/nchs/data/nhds/4procedures/2010pro4_numberprocedureage.pdf:
Centres for Disease Control and Prevention; 2010 [Available from:
http://www.cdc.gov/nchs/data/nhds/4procedures/2010pro4_numberprocedureage.pdf.
3. Association TNZO. The New Zealand Joint Registry - Eighteen Year Report. Wellington, New Zealand; 2017.

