2.2 Exclusion criteria

- Refusal or inability to consent.
- Analgesic technique involving epidural or peripheral nerve blockade (single shot or continuous techniques)
- Nerve catheter placed outside accepted range (distal to femoral triangle down to the adductor canal)
- Allergies to medication used in the study or its constituents
- Significant kidney and liver dysfunction (CrCl < 30mls/min, AST/ALT >2x upper limit of normal)

- Surgical procedure performed outside of Counties Manukau Health facilities.
- Failure to site adductor canal catheter in the appropriate location.
- Patients on >30mg/day of oral morphine equivalent for any reason.
- Patients outside the specified age range of 18-80 years.
- Patients at extremes of weight e.g.<50kg or >150kg
- If surgical team do not wish to take part or give individually tailored treatment that violate study protocol.

The Anaesthetic and Surgical management of patients enrolled in this study is largely at the discretion of the treating specialists after discussion with the patient. An anaesthetic pro forma is suggested below – data surrounding deviation from this pro forma will be collected and included in the final analysis.

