2.5 Trial Assessments

Primary outcome:

Total opioid consumption over 48 hours. This will be converted to oral morphine equivalents as per the methods prescribed by the Faculty of Pain Medicine of the Australian and New Zealand College of Anaesthetists.

(<http://fpm.anzca.edu.au/documents/opioid-dose-equivalence.pdf>)

Secondary outcomes:

- Quality of Recovery (QoR-15) scores collected 24 and 48 hours after commencement of the study infusion.
- Time to first assisted mobilisation measured in minutes after discharge from PACU.
- Passive range-of-movement on day 1 and day 2, 24 and 48 hours after commencing the study infusion.
- Number of doses of antiemetic required over the 48-hour study period.
- Hospital length of stay measured in days.
- Side effects including nausea and vomiting, pruritis and sedation (Pasero opioid-induced sedation scale) collected daily.
- “Timed up and go” or TUG test 24, 48 and 72 hours after commencement of study infusion; TUG test is the time in seconds it takes the patient to stand from the chair, walk 3 meters, turn around and sit down again.
- Passive range-of-motion; the range of knee flexion will be recorded by the research nurse using a goniometer at the same follow up time intervals.

Post-operative Analgesia:

- Regular paracetamol (1gram Q6h) and celecoxib (100mg BD) unless contraindications exist.
- Do not prescribe sustained release opioid preparations (OxyContin or M-Eslon)
- Avoid prescribing IV Morphine and Patient Controlled IV Analgesia, unless strong reasons exist (e.g. Chronic pain states or pre-existing therapy).
- Patient will have access to the following PRN analgesia if required.

- Sevredol: Morphine immediate release 10-20mg PO Q2 hours PRN
- Tramadol 50-100mg either PO or IV Q6 hours PRN
- Oxycodone Immediate release (OxyNorm): 5-10mg PO Q2 hours PRN

A trial safety and data adjudication committee with three members independent from the study will be established to adjudicate serious adverse events and determine the need to stop the administration of trial drugs. Given the established safety of the medicine and technique, it is anticipated that this should be infrequent.

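### The primary analysis described makes no use of pre-operative opioid dose, although users of up to 30 mg/day are eligible and the outcome is 48-hour opioid total in the same unit

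*Protocol*

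**What the plan says.** Protocol section 2.2 (exclusion criteria) excludes "Patients on >30mg/day of oral morphine equivalent for any reason". Use from 0 to 30 mg/day is therefore eligible.

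Section 2.5 defines the primary outcome as "Total opioid consumption over 48 hours", converted to oral morphine equivalents. It does not subtract habitual use.

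Section 3 gives the primary comparison as "a test for differences in means / variances will be performed as guided by the data". Of baseline data it says "Patient demographic, surgical and anaesthetic factors will be recorded and tabulated". It names no covariate, and neither section 2.1 nor section 2.4 names a stratification factor; randomisation is described only as 1:1 using opaque envelopes.

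Three other statements bear on the point. Section 3 also says "The statistical assessment of trial data will be devised and performed by a biostatistician". Section 2.2 says that "data surrounding deviation from this pro forma will be collected and included in the final analysis", which concerns departures from the perioperative pro forma and does not cover opioid use before admission. Section 2.5 instructs "Do not prescribe sustained release opioid preparations (OxyContin or M-Eslon)" and advises against intravenous morphine and patient-controlled analgesia "unless strong reasons exist (e.g. Chronic pain states or pre-existing therapy)".

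**The concern.** Pre-operative dose is a natural covariate here. It is fixed before randomisation, it is in the same unit as the outcome, and the eligibility rule already requires staff to ask about it. A patient who normally takes opioids may take more in the 48 hours whichever way the catheter is run. That part of the total is between-patient variation unrelated to the regimen.

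Section 1.4 leaves the sample size open but points to similar trials of 40 to 60 patients. At that size the arms can differ by chance in their number of opioid users, and an unadjusted comparison leaves that difference in the estimate. If adjustment is not fixed in advance, there may also be pressure to add it after the baseline table has been seen, in a section that already lets the data guide the choice of test.

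**Working it through.** The protocol gives no sample size, effect size, SD or proportion of opioid users, so there is no figure of its own to reproduce. Every input below except the 30 mg/day limit, the 48-hour window, the 40-60 patients, the alpha and the power is an assumption.

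**Ceiling for one patient.** 30 mg/day x 2 days = 60 mg, if the whole habitual dose continues and is counted.

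**Validity.** A simulation under no treatment effect (20,000 runs; 20% users with background spread evenly over 0-60 mg) gave the unadjusted t-test a type I error of 0.051 at 40 patients and 0.047 at 60. The mean bias was 0.15 mg and -0.04 mg, which is zero within simulation error.

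**Background variance.** Let p be the proportion of users and d the daily dose among users. With full carry-over over two days:

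Var = 4 x [p x E(d²) - (p x E(d))²]

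The grid is p = 10, 20 or 30%, with d uniform on 0-20, 10-30 or 20-30 mg/day.

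- Lowest cell (10%, 0-20 mg/day): 4 x [0.1 x 133.3 - 1²] = 49.3, SD 7.0 mg.
- Highest cell (30%, 20-30 mg/day): 4 x [0.3 x 633.3 - 7.5²] = 535, SD 23.1 mg.

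**Chance imbalance.** The SE of the between-arm difference in mean background is SD x sqrt(2/25), which is 2.0 mg in the lowest cell and 6.5 mg in the highest.

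**Gain from adjusting for dose alone.** Take a total SD of 50 mg and 25 per arm (N = 50). R² = Var/2500. Ignoring the cost of estimating the slope, the gain is 1/(1 - R²) - 1. One estimated covariate multiplies the expected variance by about (N - 3)/(N - 4) = 47/46, so the net gain is about (46/47)/(1 - R²) - 1. With half carry-over, R² falls to a quarter.

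| Cell | Carry-over | R² | Gross gain | Net gain |
|---|---|---|---|---|
| Lowest | full | 2.0% | 2.0% | -0.2% |
| Highest | full | 21.4% | 27.2% | 24.5% |
| Lowest | half | 0.5% | 0.5% | -1.6% |
| Highest | half | 5.3% | 5.7% | 3.4% |

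Simulating all nine cells (20,000 runs each) agrees: about 0 to +24 or +25% with full carry-over and about -2% to +3% with half.

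**Adding age and site.** If neither is prognostic, two more coefficients are estimated for nothing. In simulation over the same grid, the net change with full carry-over becomes -4.5% to +18.6%. With half carry-over every cell loses precision, by 0.5% to 5.5%.

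**Sensitivity to the assumed SD.** These figures assume full carry-over and ignore the cost of estimating the slope. With SD 40-80 mg, 10-50% users and background spread evenly over 0-60 mg, R² is 2-23%, and a nominal 80% power becomes about 81-89%. At 20% users and SD 60 mg, R² is 6% and power 82%. If every user were at the 60 mg ceiling, R² would be 5-56% and power 82-99%. At a standardised effect of 0.75, the number per arm falls from 28 (R² = 0) to 27 (5%), 26 (10%) or 21 (25%).

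**The case against.** The strongest case against is that covariate choice usually belongs in the statistical analysis plan. That plan is not shown, and section 3 hands the analysis to a biostatistician. This stands to the extent that the protocol's silence does not prove that no adjustment is planned. It does not dispose of the point, because section 3 does describe a primary comparison and a use for baseline data, and pre-operative dose has no part in either.

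A reader might infer three stronger things that the documents do not support.

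- **That baseline opioid use is only tabulated.** The sentence on tabulation neither mentions pre-operative opioids nor says that tabulation is the sole use.
- **That up to 60 mg of background sits in the outcome and distorts the comparison.** 60 mg is the maximum for one patient under full continuation, not a typical amount or a difference between arms. The bar on sustained-release preparations, with opioids available as needed, makes partial replacement plausible. Chance imbalance is already part of the unadjusted standard error, so the confidence interval and p-value allow for it.
- **That the covariate is already in hand.** Eligibility needs only a yes or no against 30 mg/day. Nothing in the protocol says that a figure in mg/day is recorded or names a form for it.

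It is also fair to object that adjustment can cost precision in a small trial. For dose alone the loss is about 2% at worst on this grid. For a model that adds non-prognostic age and site it is about 5-6%, which is a good reason to keep the model small.

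**Conclusion.** The point holds as a recommendation for the analysis, not as an error that invalidates the trial. The unadjusted two-group test is valid under 1:1 randomisation; what may be lost is precision and protection against chance imbalance. At 25 per arm, an assumed SD of 50 mg and 10-30% users, adjusting for pre-operative dose alone is worth about 0 to +24% in precision with full carry-over and about -2% to +3% with half. The upper end needs 30% users, all at 20-30 mg/day, with habitual use fully continued. The protocol supplies none of these inputs, so the likely benefit is modest and uncertain. Against that, the downside is about one degree of freedom, and fixing the model in advance removes a later choice about whether to adjust.

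**What to change.** Record each patient's pre-operative daily oral morphine equivalent in mg/day at the eligibility check, before randomisation, with zero entered for non-users. In section 3 or the statistical analysis plan, pre-specify the primary analysis as a linear model of 48-hour oral morphine equivalents on arm and pre-operative daily dose. Report the adjusted difference with its 95% confidence interval, and the unadjusted difference as a supporting result. The slope is estimated, so no assumption about the degree of carry-over is needed. Leave out age and hospital site unless a reason to expect them to be prognostic is written down beforehand.

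The cost is one numeric field at screening, one or two sentences of text, and about 2% of precision if the covariate proves uninformative. Eligibility, dosing and analgesic management do not change.
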